### 16.3 Other Endpoint Analyses

Follow-up Duration (in months) is calculated in the same way as PFS duration as assessed by investigator (see section 16.2.1), but the censoring rules (described in the section 16.1.1) are inverted: subjects accounted as experiencing an event for PFS are censored and those who are censored for PFS are accounted as events.

## 17 Safety Evaluation

The subsections in this section include specifications for summarizing safety endpoints that are common across clinical trials such as adverse events, laboratory tests and vital signs.

Safety analyses will be done on the safety analysis set and according to the as-treated principle.

## 17.1 Adverse Events

Treatment emergent adverse events (TEAEs) are those events that emerge during treatment having been absent pre-treatment, or worsen relative to the pre-treatment state and with onset dates occurring within the first dosing day of trial treatment (cetuximab, cisplatin, carboplatin, or 5-FU) until 30 days after the last dose of trial treatment.

All analyses described in Section 17.1 will be based on TEAEs if not otherwise specified.

Incomplete AE-related dates will be handled as follows:

- Incomplete or missing start date:
  - In case the onset date is completely missing or the onset is in the same year (if the onset year is available only) or the onset is in the same month and year (if the day is missing) as start of trial treatment, then the onset date will be replaced by the minimum of start of trial treatment date and AE resolution date (imputed, if incomplete).
  - In all other cases the missing onset day or onset month will be replaced by 1.
- Incomplete or missing stop date:
  - Incomplete stop dates will be replaced by the last day of the month (if day is missing only), if not resulting in a date later than the date of subject's death. In the latter case the date of death will be used to impute the incomplete stop date.
  - In all other cases, the incomplete stop date will not be imputed.

AEs will be coded using the latest version of Medical Dictionary for Regulatory Activities (MedDRA).

The severity of AEs will be graded by the investigator using the NCI-CTCAE version 4.03.

**Related Adverse Events** are those AEs with relationship to any trial treatment (cetuximab, cisplatin, carboplatin, or 5-FU) reported by the investigator as related or those of unknown relationship (i.e. no answer to all the questions “Relationship with Cetuximab”, “Relationship with Cisplatin”, “Relationship with Carboplatin” and “Relationship with 5-FU”). If relationship is missing the adverse event will be set to “Related” if the subject received at least one dose of given drug and the start date of adverse event is on or after the date of the first dose of this drug.

**Cetuximab related Adverse Events** are those AEs with relationship to cetuximab reported by the investigator as related or those of unknown relationship to cetuximab (i.e. no answer to the question “Relationship with Cetuximab”). If relationship is missing then the worst-case scenario is applied and the adverse event will be set to “Cetuximab Related”.

**Chemotherapy related Adverse Events** are those AEs with relationship to cisplatin or carboplatin or 5-FU reported by the investigator as related or those of unknown relationship to cisplatin (i.e. no answer to the question “Relationship with Cisplatin” or “Relationship with

Carboplatin” or “Relationship with 5-FU”). If relationship is missing then the worst-case scenario is applied and the adverse event will be set to “Chemotherapy Related”.

**Serious Adverse Events (SAEs)** are those events reported on the “Adverse Event Details” eCRF page with the “Serious Adverse Event” field ticked “Yes”.

**Adverse Events leading to cetuximab discontinuation** are those AEs with action taken regarding cetuximab reported by the investigator as “Drug withdrawn”.

**Adverse Events leading to chemotherapy discontinuation** are those AEs with action taken regarding cisplatin, carboplatin or 5-FU reported by the investigator as “Drug withdrawn”.

**Adverse Events leading to cetuximab and chemotherapy discontinuation** are those AEs with action taken regarding all the ongoing drugs (received at least one dose and not discontinued before the AE start date) reported by the investigator as “Drug withdrawn”.

**Adverse Events leading to cetuximab interruption** are those AEs with action taken regarding cetuximab reported by the investigator as “Drug interrupted”.

**Adverse Events leading to chemotherapy interruption** are those AEs with action taken regarding cisplatin, carboplatin or 5-FU reported by the investigator as “Drug interrupted”.

**Adverse Events leading to cetuximab dose reduction** are those AEs with action taken regarding cetuximab reported by the investigator as “Dose reduced”.

**Adverse Events leading to chemotherapy dose reduction** are those AEs with action taken regarding cisplatin, carboplatin or 5-FU reported by the investigator as “Dose reduced”.

**Adverse Events leading to hospitalization/prolongation** are those AEs with “Requires/prolongs hospitalization” ticked by the investigator.

**Adverse Events leading to death** are those AEs with outcome reported by the investigator as “Fatal” and/or AEs with a toxicity grade reported by the investigator as “Grade 5”.

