## 9 Changes to the Planned Analyses in the Clinical Trial Protocol

Not Applicable.

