### Safety Analysis Set

The safety (SAF) analysis set includes all subjects who received at least one dose of any trial treatment (cetuximab, cisplatin/carboplatin, or 5-FU). Analyses performed on the safety analysis set will consider subjects as treated. As soon as a subject received at least one dose of cetuximab, treatment group corresponding to cetuximab in combination with cisplatin plus 5-FU will be considered as the treatment group for this subject. If a subject receives no dose of cetuximab, then the treatment group corresponding to cisplatin plus 5-FU alone will be considered as the treatment group for this subject.

The safety analysis set will be used for safety analyses.

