### Per Protocol Analysis Set

The per protocol (PP) analysis set includes all ITT subjects who does not meet one or more of the following criteria:

- Deviations from the inclusion and exclusion criteria:
  - Inclusion criteria not fulfilled (#02): No histologically and/or cytologically confirmed diagnosis of SCCHN
  - Inclusion criteria not fulfilled (#03): No recurrent and/or metastatic SCCHN not suitable for local therapy
  - Inclusion criteria not fulfilled (#06): ECOG performance status of 0 or 1
  - Exclusion criteria fulfilled (ex#01): Prior systemic chemotherapy, except if given as part of multimodal treatment for locally advanced disease which was completed within 6 months before trial entry. (as per Protocol Amendment)
  - Exclusion criteria fulfilled (ex#03): Previous treatment with monoclonal antibody or signal transduction inhibitors targeting EGFR.
  - Exclusion criteria fulfilled (ex#04): Nasopharyngeal carcinoma.
- Randomization error:
  - Incorrect treatment group allocation, different to assignment at randomization
  - Subject randomized but did not receive any trial treatment
- Use of prohibited medication:
  - Additional concurrent chronic systemic immune treatment, chemotherapy, radiotherapy (with exceptions), hormone treatment for treatment of cancer (with exceptions), traditional Chinese medication with approval for use as anticancer treatment or any other investigational agent

- Availability of measurement of the primary endpoint:
  - No evaluable post-baseline tumor assessment (as per IRC) is available

If the Per Protocol analysis set includes at least 90% of subjects in the ITT analysis set, additional efficacy analyses on the Per Protocol analysis set and baseline analysis (including demographics) on PP/safety set will be omitted as the differences in the results based upon these two analysis sets are expected to be negligible.

| Analyses                       | Intent-to-Treat Analysis Set | Per Protocol Analysis Set | Safety Analysis Set |
|--------------------------------|------------------------------|---------------------------|---------------------|
| Demographics                   | ✓                            | ✓                         | ✓                   |
| Baseline Assessments           | ✓                            | ✓                         |                     |
| Past and Concomitant Therapies | ✓                            |                           |                     |

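### SAP 17.1 counts a blank causality answer as cetuximab- or chemotherapy-related even when the drug was never given, unlike its own rule for *Related* AEs (minor; descriptive safety tables only)

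*SAP*

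**What the plan says.** SAP 17.1 defines three causality categories in consecutive paragraphs.

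- **Related.** The category takes in events reported as related and "those of unknown relationship (i.e. no answer to all the questions" for the four drugs. A missing relationship is then set to related only "if the subject received at least one dose of given drug and the start date of adverse event is on or after the date" of that drug's first dose.
- **Cetuximab related.** A blank cetuximab answer is handled without any condition: "If relationship is missing then the worst-case scenario is applied and the adverse event will be set to" *Cetuximab Related*.
- **Chemotherapy related.** The same unconditional sentence is used. The trigger begins as "those of unknown relationship to cisplatin (i.e. no answer to the question" and goes on to list the cisplatin, carboplatin and 5-FU questions joined by 'or'.

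SAP 10.2 (Safety Analysis Set) forms the groups as treated: "If a subject receives no dose of cetuximab, then the treatment group corresponding to cisplatin plus 5-FU alone will be considered". SAP 17.1.1 and 17.2.2 tabulate all three categories by treatment group (any, serious, by grade, fatal) and do not restrict the drug-specific rows to subjects who received the drug. Protocol 8.5.4 has a single unconditional rule for missing causality, stated for trial treatment as a whole. SAP Section 9 declares no departure from the protocol.

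**The concern.** The same blank answer is treated in two ways. Under *Related* it needs exposure and a compatible onset. Under the two drug-specific categories it needs neither. Two results follow that a safety table should not show.

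First, an event can be attributed to a drug the subject never received: cetuximab in the chemotherapy-alone group or, on the 'or' reading, carboplatin in a subject who stayed on cisplatin. Carboplatin is only a replacement after cisplatin toxicity (protocol Section 6, introduction), so many subjects may never receive it.

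Second, the categories need not nest. An event can be listed as cetuximab-related or chemotherapy-related and yet be absent from the treatment-related table, which ought to contain it.

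At stake are the drug-attributed counts, including serious and fatal events, in the safety tables of a registration trial.

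**Working it through.** The plan gives no figure to reproduce. The check applies the definitions to every possible set of answers.

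**Inputs.** The four causality questions and the definitions come from SAP 17.1, and the groups from SAP 10.2. Assumptions: onset is after the first dose of every drug received; a drug received is answered related, unrelated or blank; a drug not received is answered unrelated or blank.

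**Two readings of *Related*.**
- Per-drug: any drug reported related, or blank for a drug that was received.
- All-blank: any drug reported related, or all four answers blank.

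**Single cases.**
- Cisplatin + 5-FU only, cetuximab blank, other three unrelated: *Cetuximab related* = yes; *Related* = no on either reading.
- Cetuximab + cisplatin + 5-FU, carboplatin blank, other three unrelated: *Chemotherapy related* ('or' reading) = yes; *Related* = no on either reading.
- All four blank in a treated subject with a TEAE: *Related* = yes on either reading. Non-nesting therefore needs partly blank answers.

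**Full enumeration.** Cisplatin + 5-FU only gives 3 × 3 × 2 × 2 = 36 patterns. Cetuximab + cisplatin + 5-FU gives 3 × 3 × 3 × 2 = 54.

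| Patterns flagged | Cisplatin + 5-FU (of 36) | Cetuximab + cisplatin + 5-FU (of 54) |
|---|---|---|
| Cetuximab related, as written | 18 | 36 |
| Cetuximab related, with exposure condition | 0 | 36 |
| Chemotherapy related, 'or' reading | 36 − 2 = 34 | 54 − 3 = 51 |
| Chemotherapy related, with exposure condition | 36 − 4 = 32 | 54 − 6 = 48 |
| Cetuximab related but not *Related*: per-drug / all-blank | 2 / 7 | 0 / 7 |

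The 2 are the patterns with cetuximab blank, cisplatin and 5-FU unrelated, and carboplatin either unrelated or blank. The 7 are 2 × 2 × 2 = 8 patterns with cetuximab blank and nothing reported related, less the all-blank one.

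For cisplatin + 5-FU the chemotherapy count also depends on how the trigger is read: 34 for 'or', 28 if only a blank cisplatin answer counts, 22 if all three must be blank.

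**Does correcting only the two drug-specific paragraphs suffice?** On the per-drug reading, yes. On the all-blank reading, no: cetuximab-related events still fail to nest in 7 of 54 patterns (cetuximab + cisplatin + 5-FU), and chemotherapy-related events in 11 of 36 (cisplatin + 5-FU). If all three categories are built from per-drug flags, failures are 0 of 36, 0 of 54, 0 of 54 (cisplatin, carboplatin and 5-FU) and 0 of 81 (all four drugs).

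**Against protocol 8.5.4.** If any blank counts as related, *Related* covers 35 of 36 and 53 of 54 patterns. The SAP's conditional rule, read per drug, covers 32 and 52. The SAP is therefore already narrower than the protocol.

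These are counts of logically possible patterns. They show where the definitions disagree and say nothing about how often.

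**The case against.** **The unconditional rule is the conservative one, and the protocol uses it.** Part of this stands. The sentence that departs from protocol 8.5.4 is the conditional one under *Related*, so the departure already exists and the correction does not create it. Nesting could also be restored by making *Related* unconditional. That would still credit events to a drug never given, and the protocol's rule concerns trial treatment as a whole, so it does not support such an attribution.

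**A reader might infer that the rule narrows the displayed difference between arms in cetuximab toxicity.** The documents do not support this. The between-group displays in SAP 17.1.1 use all TEAEs, Grade 3 or higher TEAEs and SAEs. Those in SAP 17.2.4 use the tier categories. None is defined by relatedness, and protocol 8.5.4 plans no formal comparisons. With dosing as planned, the cetuximab group's own cetuximab-related count does not change (36 of 54 patterns either way). A cetuximab-related count in an unexposed column would also be conspicuous.

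**The unclear triggers are largely editorial.** This mostly stands. The SAP's reference to a given drug favours the per-drug reading. The cisplatin phrase looks like a remnant of the change, recorded in the SAP's modification history, from separate chemotherapy drugs to one combined category. A programmer still has to choose, so the text should settle it.

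**Late cetuximab.** A reader might infer that counts in the cetuximab group are inflated too, because SAP 10.2 foresees "Incorrect treatment group allocation, different to assignment at randomization" and states "As soon as a subject received at least one dose of cetuximab, treatment group corresponding to cetuximab in combination" therapy applies. Nothing there says cetuximab would start late in such a subject, so this remains hypothetical.

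**The onset condition has a side effect.** This stands. Outside the month in which trial treatment starts, SAP 17.1 imputes a missing onset day as 1. An AE in the month of a carboplatin switch could then be placed before the first carboplatin dose and lose its conservative flag. The fix has to deal with this.

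**Conclusion.** Wrong as written, and minor. The two drug-specific definitions lack the exposure and onset condition that the neighbouring definition carries, and no other section supplies it. The consequence is spurious counts for drugs not given in the cetuximab-related and chemotherapy-related rows of SAP 17.1.1 and 17.2.2. With partly blank answers, some of those events can also be missing from the treatment-related table.

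The size is unknown. The eCRF answer options are not shown, and protocol 7.4.1.1 requires investigators to assess causality systematically. If no blanks occur, the effect is nil. A reader might take the planned chemotherapy-alone arm, 240/3 = 80 subjects, as an estimate. It is only the arm's size: reaching it would need every one of those subjects to have a TEAE with a blank cetuximab answer, and nothing in the documents indicates that. Nor can the pattern counts be read as rates.

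Efficacy, the deaths table based on the death-report page, and the special-category and tier summaries are unaffected. The carboplatin part rests on the 'or' reading of the chemotherapy trigger.

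**What to change.** 1. Define one flag for each of cetuximab, cisplatin, carboplatin and 5-FU. The flag is set if the investigator reported the event as related, or if the answer is blank, the subject had at least one dose of that drug, and onset was on or after its first dose.
2. Set *Cetuximab related* to the cetuximab flag, *Chemotherapy related* to any of the cisplatin, carboplatin or 5-FU flags, and *Related* to any of the four. This replaces both unclear triggers, and nesting then holds by construction.
3. State that when a partial AE onset date cannot exclude onset on or after that drug's first dose, the onset condition counts as met. Day-1 imputation then cannot remove the conservative flag.
4. In SAP Section 9, "Changes to the Planned Analyses in the Clinical Trial Protocol", record that the conditional rule, already in use for *Related*, is narrower than the unconditional rule in protocol 8.5.4.

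Cost: three reworded definitions, one sentence on partial dates, one Section 9 entry and an update to the derivation. No new data are needed. If the all-blank reading of *Related* was intended, the treatment-related table changes as well.

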### 17.1.1 All Adverse Events

Adverse events will be summarized by worst severity (according to NCI-CTCAE version 4.03) per subject, using MedDRA (latest version) PT as event category and MedDRA (latest version) SOC body term as Body System category.

Adverse events will be displayed in terms of frequency tables: PT and primary SOC in alphabetical order.

If an adverse event is reported for a given subject more than once during treatment, the worst severity and the worst relationship to trial treatment will be tabulated.

In case a subject had events with missing and non-missing grades, the maximum of the non-missing grades will be displayed.

An overview table of TEAEs will be provided detailing the number and percentage of subjects with:

- Any TEAE
- Any trial treatment related TEAE
- Any cetuximab related TEAE
- Any chemotherapy related TEAE
- Any serious TEAE
- Any non-serious TEAE
- Any trial treatment related serious TEAE
- Any cetuximab related serious TEAE
- Any chemotherapy related serious TEAE
- Any TEAE by worst NCI-CTCAE severity grade
- Trial treatment related TEAE by worst NCI-CTCAE severity grade
- Cetuximab related TEAE by worst NCI-CTCAE severity grade
- Chemotherapy related TEAE by worst NCI-CTCAE severity grade
- Any TEAE leading to death
- Any trial treatment related TEAE leading to death
- Any cetuximab related TEAE leading to death
- Any chemotherapy related TEAE leading to death

Tables for TEAEs frequency corresponding to each category in the overview table above will be provided for actions by MedDRA primary SOC (ordered alphabetically) and PT (ordered alphabetically), each subject will be counted only once within each PT or SOC.

#### **Clinical trial.gov and EudraCT -requirements**

- Summary tables for non-serious adverse events excluding SAEs applying frequency threshold of 5% will be provided.

Besides this, the following tables will also be generated:

- TEAEs with  $\geq 10\%$  difference between treatment groups
- TEAEs Grade  $\geq 3$  with  $\geq 5\%$  difference between treatment groups
- SAEs with  $\geq 5\%$  difference between treatment groups

All TEAEs will be listed to support these tables.

A listing of TEAEs leading to death will also be provided including all relevant information.

## 17.1.2 Adverse Events Actions

An overview table will be provided for TEAEs actions as following:

- Adverse Events leading to any trial treatment discontinuation
- Adverse Events leading to cetuximab discontinuation
- Adverse Events leading to chemotherapy discontinuation
- Adverse Events leading to both cetuximab and chemotherapy discontinuation
- Adverse Events leading to trial treatment interruption.
- Adverse Events leading to cetuximab interruption.
- Adverse Events leading to chemotherapy interruption
- Adverse Events leading to trial treatment dose reduction
- Adverse Events leading to cetuximab dose reduction
- Adverse Events leading to chemotherapy dose reduction
- Adverse Events leading to hospitalization/prolongation.

Tables for TEAEs frequency corresponding to each category in the overview table above will be provided for actions by MedDRA primary SOC (ordered alphabetically) and PT (ordered alphabetically), each subject will be counted only once within each PT or SOC.

A listing of TEAEs actions including all relevant information will also be provided.

## 17.2 Deaths, Other Serious Adverse Events, and Other Significant Adverse Events

### 17.2.1 Deaths

All deaths, deaths within 30 days after last dose of trial treatment (cetuximab, cisplatin, carboplatin, or 5-FU), deaths within 60 days after first dose of trial treatment as well as the primary reason for death, will be tabulated based on information from the “Report on Death” eCRF page:

- Any subject who died and primary reason for death
  - Progressive disease and/or disease related condition
  - Related to trial treatment(s)
    - Cetuximab
    - Cisplatin
    - Carboplatin
    - 5-FU
  - Event unrelated to trial treatment

- Unknown
- Subjects who died within 30 days after last dose of treatment and primary reason for death
  - Progressive disease and/or disease related condition
  - Related to trial treatment(s)
    - Cetuximab
    - Cisplatin
    - Carboplatin
    - 5-FU
  - Event unrelated to trial treatment
  - Unknown
- Subjects who died within 60 days after first dose of treatment and primary reason for death
  - Progressive disease and/or disease related condition
  - Related to trial treatment(s)
    - Cetuximab
    - Cisplatin
    - Carboplatin
    - 5-FU
  - Event unrelated to trial treatment
  - Unknown

In addition, date and cause of death will be provided in individual subject data listing together with selected dosing information (date of first / last administration, separately for cetuximab, cisplatin, carboplatin, and 5-FU).

This listing will also include:

- Data from “Report on Death” eCRF page
- Flag for death within 30 days after last dose of trial treatment
- Flag for death within 60 days after first dose of trial treatment

## 17.2.2 Serious Adverse Events

The following summary tables will be provided for serious TEAEs detailing the number and percentage of subjects by MedDRA primary SOC (ordered alphabetically) and PT (ordered alphabetically); each subject will be counted only once within each PT or SOC:

- Serious TEAEs.

- Trial treatment related serious TEAEs.
- Cetuximab related serious TEAEs
- Chemotherapy related serious TEAEs

A listing of serious TEAEs will also be provided including all relevant information.

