7.4.1.3 Definition of the Adverse Event Reporting Period

The AE reporting period for safety surveillance begins when the subject is initially included in the trial (date of first signature of informed consent) and continues until the Safety Follow-up visit.

Any SAE assessed as related to cetuximab must be reported whenever it occurs, irrespective of the time elapsed since the last administration of cetuximab.

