## 8 Overview of Planned Analyses

The main statistical analysis of data is event driven and is expected to be approximately 22 months after trial initiation (i.e., after the 144 independently-assessed PFS events with respect to the primary endpoint have occurred).

The final analysis of OS (OS cut-off date should be after at least 180 deaths [e.g., 75% of randomized subjects] have been reported, or up to 12 months after the last subject is randomized, whichever is earlier), will be presented in a clinical trial report addendum. Safety data collected after the OS cut-off will be reported using patient profiles. No additional statistical analyses will be conducted.

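### Non-fatal cetuximab-related SAEs starting more than 30 days after the last dose of any trial treatment, and before the OS cut-off, must be reported under Protocol 7.4.1.3 but have no SAE output in SAP 17.1.1 or 17.2.2

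*SAP*

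**What the plan says.** Protocol 7.4.1.3 ends ordinary adverse event reporting at the Safety Follow-up visit, then makes one exception: "Any SAE assessed as related to cetuximab must be reported whenever it occurs, irrespective of the time elapsed since the last administration of cetuximab".

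SAP 17.1 defines a TEAE as an event with onset from the first dosing day "until 30 days after the last dose of trial treatment". It then sets the default for its own section: "All analyses described in Section 17.1 will be based on TEAEs if not otherwise specified". The serious-event rows in the 17.1.1 overview are worded as serious TEAEs, and the supporting listing is also restricted: "All TEAEs will be listed to support these tables".

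SAP 17.2.2 specifies four tables (all, trial-treatment-related, cetuximab-related and chemotherapy-related), all for serious TEAEs, and one listing: "A listing of serious TEAEs will also be provided including all relevant information". By contrast, the SAP's definition of an SAE in 17.1 rests on a seriousness field on the adverse event eCRF page and has no time condition.

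Two neighbouring groups do have an output. The death table in SAP 17.2.1 has a row for "Any subject who died and primary reason for death", with no time limit. For the period after the OS cut-off, SAP 8 states: "Safety data collected after the OS cut-off will be reported using patient profiles".

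**The concern.** Delayed serious events attributed to the study drug are the one category that the protocol singles out for open-ended reporting. Followed as written, the SAP gives these events no place in its SAE outputs unless they are fatal or are collected after the OS cut-off. Safety is a secondary objective. A reader of the SAE tables and listing could not tell whether there were no late cetuximab-related SAEs or whether they had simply not been displayed.

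**Working it through.** No figure in the plan needs reproducing. The check follows one event through every output that could show it: a non-fatal SAE, attributed to cetuximab, with onset on Day 31 or later after the last dose of trial treatment and before the OS cut-off.

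| Place | Rule | Is the event shown? |
|---|---|---|
| Protocol 7.4.1.3 | Cetuximab-related SAEs, no time limit | Reportable |
| SAP 17.1 | TEAE window closes at 30 days | Not a TEAE |
| SAP 17.1.1 serious rows and AE listing | TEAEs only | No |
| SAP 17.1.2 actions, including hospitalization | TEAEs only | No |
| SAP 17.2.1 deaths | Fatal events | No (non-fatal) |
| SAP 17.2.2 SAE tables | Serious TEAEs | No: 0 of 4 |
| SAP 17.2.2 SAE listing | Serious TEAEs | No: 0 of 1 |
| SAP 17.2.3 and 17.2.4 | Some summaries state no TEAE limit | Perhaps counted, but not identified as serious and cetuximab-related |
| SAP 8 patient profiles | Data after the OS cut-off | No (earlier) |

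**Two clocks.** Protocol 7.4.1.3 counts from the last cetuximab dose, whereas the TEAE window counts from the last dose of any trial treatment. A cetuximab-related SAE occurring long after cetuximab was stopped is still a TEAE while chemotherapy continues. The gap opens only 30 days after the last dose of any trial drug.

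**The one table worded simply as SAEs.** SAP 17.1.1 includes a table of SAEs differing by at least 5% between groups. It sits inside Section 17.1, so the TEAE default applies. Suppose that default did not apply, and take the planned numbers as denominators:

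- Arm A: 240 × 2/3 = 160 subjects.
- With none affected in Arm B, a term appears from 0.05 × 160 = 8 Arm A subjects.

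Isolated late events would not reach that threshold.

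**Likely size.** The documents give no rate of late cetuximab-related SAEs, so no count can be estimated. Protocol 3.7.1 gives a mean half-life of 112 hours (range 63 to 230). Thirty days is 30 × 24 = 720 hours. Assuming first-order decay from the last cetuximab dose:

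- 112 h: 720/112 = 6.4 half-lives, and 0.5^(720/112) leaves about 1.2%.
- 230 h: 720/230 = 3.1 half-lives, and 0.5^(720/230) leaves about 11.4%.

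This describes remaining exposure, not event risk, but it suggests few events.

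**Are the events in the eCRF?** Probably, but this is not guaranteed. Pointing towards capture:

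- Adverse events are documented at the 6-weekly visits (Protocol 7.1.4) and at the EOEA visit (7.1.5), which may fall after the Safety Follow-up visit.
- Table 1.1 appears to mark adverse events at survival follow-up.

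Pointing the other way:

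- Protocol 7.4.1.2 asks for eCRF data over the reporting period, which 7.4.1.3 ends at the Safety Follow-up visit.
- Protocol 7.4.1.4 frames the SAE Report Form procedure around new SAEs within that period.
- Protocol 7.1.7 lists resolution of ongoing SAEs at survival follow-up but no query for new ones.

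**The case against.** The strongest defence is that the SAP does what the protocol's statistics section asks. Protocol 8.3.3 names treatment-emergent SAEs as the safety endpoint, and 8.5.4 uses the same 30-day window. Section 7.4.1.3 is a surveillance duty owed by the investigator to the sponsor, and nothing promises that every reportable event will be tabulated. This stands as far as the tables are concerned: they match the protocol and should not change. A reader might infer that the SAP contradicts the protocol's analysis plan, and the documents do not support that. The defence does not supply an output for events that the same protocol requires to be reported.

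A reader might also infer that these events will be missing from the trial report or hidden from the sponsor. That is not supported either. They must still be reported, Protocol 10.6.1 ties the report to ICH E3, and SAP 5 allows unplanned analyses if they are identified as such. What remains is that nothing in the SAP requires them to be shown.

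A third objection concerns the remedy. It is tempting to print a count straight from the clinical database, even when it is zero. Because eCRF capture is not assured, such a zero could stand beside cases that the sponsor holds only on SAE Report Forms. The consistency rule in Protocol 7.4.1.4 does not prevent this: it requires the form to agree with what the eCRF records about an event, not that every event be in the eCRF. This objection stands in full and shapes the fix.

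**Conclusion.** The gap is real but narrow: SAE display for non-fatal cetuximab-related events starting more than 30 days after the last dose of any trial treatment and before the OS cut-off. The practical effect is probably small, and its size cannot be stated because no event rate is given. No endpoint, the 0.77 hazard ratio criterion or any between-arm TEAE comparison is affected, and subject safety is not at stake. The conclusion rests on reading the TEAE default in SAP 17.1 as covering all of 17.1.1, and on the explicit wording of 17.2.2. This is a low-priority improvement, worth making because it costs little.

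**What to change.** In SAP 17.2.2, replace the listing of serious TEAEs with a listing of all SAEs up to the data cut-off. It should show a treatment-emergent flag, relationship to cetuximab, and days to onset from both the last dose of trial treatment and the last dose of cetuximab.

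State that this listing is reconciled with the sponsor's safety database before lock, so that late SAEs held only on SAE Report Forms are included.

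After that reconciliation, and not before, give one descriptive Arm A count: cetuximab-related SAEs with onset more than 30 days after the last dose of trial treatment. Add a note that it has no Arm B counterpart, because open-ended reporting applies only to cetuximab. Leave the serious-TEAE tables unchanged.

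The cost is SAP wording, a wider listing, one extra count and one reconciliation check. The report may show a few more SAEs attributed to cetuximab.
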